6. GENERAL ANALYSIS DEFINITIONS

6.1 TREATMENT(S)

The following treatment option is planned in the study:

- [REDACTED] Dose [REDACTED] : spesolimab [REDACTED]
- [REDACTED] Dose [REDACTED] : spesolimab [REDACTED] at Day [REDACTED] and Day [REDACTED]

The study phases are defined relative to spesolimab at Day 1 as below:

Table 6.1: 1 Flow chart of analysis phases of the study for each flare

Study analysis phase	Description	Start (included)	End (included)
Screening phase	Screening	Earliest of i) Date of informed consent, ii) first screening procedure	Date/time of start of [REDACTED] minus 1 minute
Treatment phase (including REP if applicable)	On-treatment period	Date/time of start of [REDACTED] (Day 1)	Earliest of: i) Date of end of last [REDACTED] + 112 days at 23:59, ii) Date of end of study visit, iii) Date/time of start of screening for next flare
Follow-up phase ¹	Off-treatment period	Date of end of [REDACTED] of last study treatment + 113 days at 0:00 a.m.	Latest of: i) Date of EOS visit; ii) Last contact date on End of Study page at 23:59

Dates are defined individually per patient. REP represents the residual effect period. An analysis phase will not extend beyond the start date of the following phase.¹ The follow-up phase only exists if the last contact date is after the date of [REDACTED] of last study drug + 112 days.

Note that in the trial, a patient experiencing a new GPP flare may re-enter the study within/after the [REDACTED]-week follow-up period, starting from screening again. For details, refer to section 3.1 in CTP. Therefore, a patient may have more than one screening/flare treatment/follow-up period.

Data across all flare treatment periods will be pooled and handled per patient, with "Overall Speso [REDACTED]" to label the treatment group.

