7. PLANNED ANALYSIS

For End-Of-Text (EoT) tables, the set of summary statistics is N / Mean / SD / Min / Q1 / Median / Q3 / Max.

For tables that are provided for endpoints with some extreme data, median, quartiles and percentiles should be preferred to mean, standard deviation, minimum and maximum.

Tabulations of frequencies for categorical data will include all possible categories and will display the number of observations in a category as well as the percentage (%) relative to the respective treatment group (unless otherwise specified, all patients in the respective patient set whether they have non-missing values or not).

The precision for percentages should be one decimal point, unless the denominator is smaller than 100 (in all treatment columns), in which case percentages are given in integer numbers. The category “missing” will be displayed only if there are actually missing values.

Disposition of the patient population participating in the trial will be summarised by the presentation of the frequency of patients enrolled, enrolled but not treated, enrolled and treated, who completed participation in the trial, and who were prematurely discontinued from trial, by reason. The iPDS, baseline conditions/medical history, demographic/baseline characteristics, concomitant medications, concomitant non-drug therapies, exposure will be presented based on TS for the entire trial duration. In addition, the number of flares will also be summarized based on TS.

For safety data, per patient analysis based on patient will be used for the analysis, whose denominator will be the number of patients or time at risk per patient for all applicable periods.

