7.7 EXTENT OF EXPOSURE

Treatment exposure is defined as the total dose of randomized spesolimab [mg] received per patient. In general, the total dose of spesolimab [mg] received per [REDACTED] is calculated as the

total [REDACTED] volume [mL], as documented on the eCRF, times the strength prepared in the [REDACTED]

Strength in [REDACTED]
[REDACTED]

The duration of the [REDACTED] trial treatment [minutes] at each visit will be calculated as the end of the [REDACTED] date/time minus the start of the [REDACTED] date/time.

The number of doses will be calculated, which is based upon the number of visits at which doses of study drug were administered.

Time at risk will be assessed in months per definition in [Section 7.8.1](#), where the end date will be the end of each flare treatment period in [Table 6.1: 1](#).

The duration of [REDACTED], the number of doses, time at risk and the total dose [mg] will be summarised by descriptive statistics (N, mean, SD, minimum, Q1, median, Q3, maximum), using per patient analysis for all flare treatment period.

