7.8 SAFETY ANALYSIS

All safety analyses will be performed following BI standards. No hypothesis testing is planned.

For all flare treatment period (all flares for a patient combined) based on TS, the AE data and possibly clinically significant laboratory abnormalities will be analysed under OR (as defined in [Section 6.6](#))

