7.8.1 Adverse Events

AEs will be coded with the most recent version of MedDRA. Patients will be analyzed according to the actual treatment received.

The analysis of AEs will be based on the concept of treatment emergent AEs. This means that all AEs will be assigned to the screening phase, treatment phase or follow-up phase as defined in [Section 6.1](#). Since only the start date of an AE is collected (without start time), any AE occurrence on the same day as spesolimab at Day 1 will be assigned to the on-treatment period.

The primary endpoint of occurrence of treatment emergent adverse events (TEAE), will be analysed as the exposure-adjusted adverse event incidence rates in all flare treatment period based on TS by using per patient analysis for TEAE.

Per patient analysis for TEAE

- 1) The exposure adjusted incidence rate (per 100 patient years) of a selected treatment emergent adverse event is defined as the number of patients experiencing the adverse event per treatment group during time at risk divided by the total time of patients at risk in that treatment group to contribute the event to the analysis multiplied by 100 (per 100 patient years).

Time at risk [patient years] = (date of onset of AE – first treatment start date within that treatment period + 1) / 365.25

For all flare treatment period on a patient level, each flare treatment period is combined with the previous flare treatment period as defined in [Section 6.1](#).

- 2) If, for a patient, the selected treatment emergent adverse event didn't occur during the above defined treatment period (per [Section 6.1](#)) then the time at risk will be censored at the earliest of date of death, last contact date per EoS page, or the end of the above defined treatment period.

For each selected treatment emergent AE, the exposure adjusted incidence rate will be calculated as:

Incidence rate [1/100 Patient years (pt-yrs)] = 100 * number of patients with TEAE / Total TEAE-specific time at risk [patient years].

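### The time-at-risk formula in SAP 7.8.1, applied to all flares combined, does not carry out the SAP's own definition of the denominator for re-treated patients

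*SAP*

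**What the plan says.** SAP 6.1 recognises that "a patient may have more than one screening/flare treatment/follow-up period" and states that "Data across all flare treatment periods will be pooled and handled per patient". Table 6.1: 1 defines the phases separately for each flare. The on-treatment period starts on Day 1 and ends at the earliest of last dose + 112 days, the end-of-study visit, or the start of screening for the next flare.

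SAP 7.8 sets the scope of the adverse-event analysis: "For all flare treatment period (all flares for a patient combined) based on TS". SAP 7.8.1 makes the exposure-adjusted incidence rate over that combined period the analysis of the primary endpoint. It describes the denominator in words as the time during which patients are at risk of contributing the event. The printed formula is the AE onset date minus "first treatment start date within that treatment period + 1) / 365.25". For several flares the only instruction is that "each flare treatment period is combined with the previous flare treatment period as defined in" Section 6.1. Patients without the event are censored at the earliest of death, "last contact date per EoS page, or the end of the above defined treatment period".

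Two other places bear on the intent. SAP 7 describes a per-patient analysis "whose denominator will be the number of patients or time at risk per patient for all applicable periods". SAP 7.7 says "Time at risk will be assessed in months per definition in" Section 7.8.1, with the end date taken at the end of each flare treatment period.

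**The concern.** In the combined period, the earliest treatment start date is Day 1 of flare 1. A single subtraction from that date includes every day in between. If a patient re-enters after the first follow-up has ended, the days between flares become time at risk, although Table 6.1: 1 does not place them on treatment. An event with onset on those days is not treatment-emergent. Under Protocol 5.2.4.2.1, AEs are also not actively monitored after a patient's end of program, and those still reported stay out of the CRF. Such days can add to the denominator but not to the numerator.

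The censoring rule adds a second uncertainty. Protocol 6.1.3 has a completion page filled in at the end of follow-up and lets the patient re-enter under the same number, so a re-treated patient may have more than one end-of-study record. Taking the earliest last-contact date could stop an event-free patient's time at flare 1.

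At stake is the primary-endpoint rate, together with the same rate for SAEs and AESIs. The SAP governs three trials, so different programmers could read the text differently.

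**Working it through.** The documents give no person-years, event counts, re-treatment share or gap length, so there is no planned figure to reproduce. The check compares denominators for the same events.

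**Single patient, one dose per flare.** Day 1 to Day 1 + 112 is L = 113 on-treatment days. Take a 180-day gap (assumed).
- Event-free through two flares: summed 113 + 113 = 226 days; span 226 + 180 = 406 days; rate ratio 226/406 = 0.56.
- First SAE on day 10 of flare 2: summed 113 + 10 = 123 days; span 113 + 180 + 10 = 303 days.
- Event-free, but censored at the flare 1 record: 113 days instead of 226.

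**Cohort illustration.** Hazards come from the phase II spesolimab arm in Protocol 1.2.3 (19 patients = 54.3%, so n = 35). Any AE: 77.1% = 27/35 at week 1 and 91.4% = 32/35 at week 12. SAE: 14.3% = 5/35 and 25.7% = 9/35. The week-12 figures include patients re-dosed at day 8. Two hazard shapes are used: constant over 84 days, or piecewise with a break at day 7. The hazard is assumed to restart at flare 2.

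S is the probability of being event-free after 113 days, and T is the expected at-risk days per flare. For a constant hazard h, S = exp(-113h) and T = (1 - S)/h.

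| Event | Hazard | S | T (days) |
|---|---|---|---|
| Any TEAE | constant | 0.037 | 32.9 |
| Any TEAE | piecewise | 0.059 | 17.0 |
| SAE | constant | 0.670 | 93.1 |
| SAE | piecewise | 0.704 | 89.0 |

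With p the share re-treated once and g the gap, expected days per patient are:
- Summed on-treatment days: D0 = T + pST
- Span for all: D1 = T + pS(T + g)
- Event-free re-treated patients censored at flare 1, flare 2 events over the span: D2 = T + pS[(T - SL) + (1 - S)g]

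Event counts are the same throughout, so the relative error of the rate is D0/D1 - 1 or D0/D2 - 1.

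Worked case: SAE, constant hazard, p = 0.2, g = 180, so pS = 0.2 × 0.6704 = 0.1341.
- D0 = 93.14 + 0.1341 × 93.14 = 105.6
- D1 = 105.63 + 0.1341 × 180 = 129.8; error 105.6/129.8 - 1 = -18.6%
- D2 = 93.14 + 0.1341 × [(93.14 - 75.76) + 0.3296 × 180] = 103.4; error +2.1%

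| Event (p = 0.2, g = 180) | D0 | D1 | Error | D2 | Error |
|---|---|---|---|---|---|
| Any TEAE, constant | 33.2 | 34.5 | -3.8% | 34.4 | -3.6% |
| Any TEAE, piecewise | 17.2 | 19.3 | -11.1% | 19.1 | -10.1% |
| SAE, constant | 105.6 | 129.8 | -18.6% | 103.4 | +2.1% |
| SAE, piecewise | 101.5 | 126.8 | -20.0% | 97.8 | +3.8% |
| Rare AESI (limit) | 135.6 | 171.6 | -21.0% | 113.0 | +20.0% |

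**No gap (g = 0, p = 0.2).** D1 equals D0, so the error is zero. Under D2 it is not. For SAE with constant hazard, D2 = 93.14 + 0.1341 × 17.38 = 95.5 and the error is +10.6%; with piecewise hazard it is +12.4%. For a rare AESI, D0/D2 = 113(1 + p)/113, so the error equals p, here +20%, whatever the gap. Any TEAE moves by less than 1%.

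**Range for D1** over p = 10-30% and g = 90-180 days: any TEAE 1-6% low (constant) or 3-16% low (piecewise), SAE 6-26% low, rare AESI 7-27% low.

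**Mixed reading.** If only flare 2 events are measured over the span and event-free patients are summed correctly, then at p = 0.2 and g = 180 the SAE rate is 7% low and the rare AESI rate is essentially right.

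**The case against.** The best defence is that a sum was meant all along. A flare can involve two doses, so the first treatment start within a treatment period may simply mean that flare's Day 1, with the next sentence then joining the flare periods. The verbal denominator, the reference to Section 6.1, the wording in SAP 7 on all applicable periods and the per-flare end date in SAP 7.7 all fit this. It is persuasive on intent, and a reader should not conclude that the SAP has deliberately chosen a calendar-span analysis. It does not settle execution: SAP 7.7 sends the reader back to 7.8.1 for the definition, and 7.8.1 prints one subtraction with no rule for adding periods or removing gaps. Some SAP sections are redacted and the cited sponsor AE standards are not available, so the claim covers visible text only.

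A reader might also infer that the rates must be understated, or that nothing goes wrong when there is no gap. The documents support neither. Both depend on which end-of-study record the censoring rule takes, and the no-gap result fails if it takes the flare 1 record.

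The point about limited weight stands. The program is single-arm and descriptive, with no hypothesis test. The largest percentages concern SAEs and AESIs, which are secondary endpoints. Counts of patients and of flare periods with events are reported alongside and do not change.

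**Conclusion.** The point holds as a mismatch between formula and definition: the line printed in SAP 7.8.1 does not deliver the denominator that the section describes, and the censoring rule does not say which record applies after re-entry. What will actually be programmed cannot be known from the documents.

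The distortion is limited to re-treated patients who are still free of the analysed event when flare 1 ends. Patients with one flare and first events in flare 1 are unaffected. With 20% re-treated and a 180-day gap, the rates are low by 4-11% (any TEAE), 19-20% (SAE) and 21% (rare AESI) if event-free patients are measured over the span. If they are censored at the flare 1 record while flare 2 events use the span, any TEAE is 4-10% low, SAE 2-4% high and rare AESI 20% high; with no gap, SAE is still 11-12% high and rare AESI 20% high. These sizes rest on the assumed share and gap and on hazards borrowed from the phase II arm. The weight is low to moderate.

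**What to change.** State in SAP 7.8.1 that time at risk for the all-flare analysis is the sum of on-treatment days over a patient's flare treatment periods as defined in Table 6.1: 1, up to and including the day of first onset or censoring, divided by 365.25. Days outside any on-treatment period are excluded. State also that each flare period is censored using that flare's own last-contact or end-of-study record, so that an earlier flare's record does not end time in a later one. Use the same definition for the time-at-risk summary in 7.7.

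The cost is SAP wording and a few lines of code, applied consistently across the three trials that the SAP covers. No new data or tables are needed.

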7.8.2 Laboratory data

Clinically relevant findings in laboratory data will be reported as baseline conditions (at screening) or as AEs (during the trial) if judged clinically relevant by investigator, and will be analyzed as such.

7.8.3 Vital signs

Clinically relevant findings in vital signs data will be reported as baseline conditions (at screening) or as AEs (during the trial) if judged clinically relevant by the investigator, and will be analyzed as such.

7.8.4 ECG

Abnormal findings in 12-lead ECG will be reported as baseline conditions (at screening) or as AEs (during the trial) if judged clinically relevant by investigator, and will be analyzed as such. No separate listing or analysis of ECG data will be prepared.

7.8.5 Others

Local Tolerability will be summarized at Day 1 and Day 8, with the frequency and percentage of patients/flare treatment periods who experienced any reaction presented by symptom and severity of reaction.

**8. TIMEPOINT OF RELEASE OF TREATMENT
INFORMATION**

The treatment information will be loaded into the trial database at trial initiation.

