At week 1, 19 patients (54.3%) randomized to spesolimab versus one patient (5.6%) randomized to placebo achieved a GPPGA pustulation subscore of 0 (no visible pustules; risk difference, 48.7; 95% CI, 21.5–67.2; one-sided $P<0.001$). A GPPGA total score of 0 or 1 (clear or almost clear skin) at week 1 was achieved in 15 patients (42.9%) randomized to spesolimab versus two patients (11.1%) randomized to placebo (risk difference, 31.7; 95% CI,

Proprietary confidential information © 2022 Boehringer Ingelheim International GmbH or one or more of its affiliated companies

2.2–52.7; one-sided $P=0.012$). Clinical responses were observed regardless of *IL36RN* mutation status. At week 4, 16 patients (45.7%) receiving a single spesolimab dose at day 1 achieved a GPPASI 75 versus two patients (11.1%) receiving placebo (risk difference, 34.6; 95% CI, 5.8–55.4; one-sided $P=0.008$). Additionally, significantly higher reductions in pain VAS ($P=0.001$) and PSS ($P=0.004$), and improvement in FACIT-Fatigue scores ($P=0.001$) at week 4 were achieved by patients receiving spesolimab versus those receiving placebo.

At day 8, 12 patients randomized to spesolimab received an open-label (second) dose of 900 mg spesolimab. Beyond day 8, response rates in patients in the spesolimab arm who received one or two doses continued to increase. A total of 23 patients (65.7%) achieved a GPPGA pustulation subscore of 0 by week 2, and the same proportion achieved a GPPGA total score of 0 or 1 by week 4. These were sustained in at least 60% of patients up to week 12. The median percent improvement in the GPPASI score from baseline was 42.8% at week 1 and progressively increased up to 81.8% at week 12. A GPPASI 75 was achieved in 13 patients (37.1%) at week 2, in 18 patients (51.4%) at week 4, and in 21 patients (60.0%) at week 8, and was sustained up to week 12. Rapid reductions in pain VAS score and improvements in DLQI scores were achieved through week 4 and sustained through week 12. CRP normalized within 4 weeks in patients with elevated baseline CRP (≥ 10 mg/L), who received one or two doses of spesolimab.

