3. DESCRIPTION OF DESIGN AND PROGRAM POPULATION

3.1 OVERALL PROGRAM DESIGN AND PLAN

This is an open-label, multi-centre, single-arm trial, designed to provide early access to spesolimab, for patients with GPP presenting with a flare and for whom no satisfactory authorised alternative therapy exists and who are unable to participate in a clinical trial, as assessed by the treating physician.

After signing informed consent and if all eligibility criteria are met, patients will receive a [REDACTED] spesolimab. If deemed necessary by the treating physician (i.e. if the flare symptoms persist), a [REDACTED] spesolimab may be administered [REDACTED] after the initial [REDACTED].

If [REDACTED] is administered, then patients will visit the treating physician approximately at week [REDACTED], week [REDACTED] and week [REDACTED]. If a [REDACTED] may be given, then the dates that patients will visit the treating physician is changed to approximately at [REDACTED] [REDACTED] after initial dose of spesolimab. Please refer to section [6.1](#) for details on the program visit procedures. Patient's participation in the program will end after conclusion of the [REDACTED]-week follow-up period after the last [REDACTED] / drug administration.

If a patient experiences a new GPP flare (following the resolution of a previous flare with spesolimab treatment) after the [REDACTED]-week follow-up period the patient may re-enter in the program and be treated again with spesolimab, providing eligibility criteria are still met and the overall program is still running. The same dosing and follow-up requirements apply as for the previous flare.

In the situation that a patient experiences a new GPP flare within the [REDACTED]-week follow-up period and the physician wishes to treat this new flare with spesolimab, eligibility needs to be assessed and agreed upon with the BI clinical team.

The enrolment of patients for the program will stop at the time spesolimab becomes commercially available or 6 months after marketing authorization for treatment of GPP in China (whichever is earlier). The overall program will close when the last patient completes the follow up period after the last [REDACTED] of spesolimab or if any other reason listed in section [3.2.4.3](#) is met.

Below is suggested flow chart for patient visit.

Flow Chart

Trial Period	Screening	Treatment		Follow-up Period		
Visit	V1 ¹	V2 ¹	V3 ²	V4	V5	V6/EoS ³
Week [REDACTED]) ²						
Week [REDACTED]) ²						

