Window			±1d	±1d	±7d	±7d
Informed consent	X					
Demographics	X					
Medical history	X					

Proprietary confidential information © 2022 Boehringer Ingelheim International GmbH or one or more of its affiliated companies

Trial Period	Screening		Treatment		Follow-up Period	
	V1 ¹	V2 ¹	V3 ²	V4	V5	V6/EoS ³
Visit						
Week [REDACTED] ²						
Week [REDACTED] ²						
Window			±1d	±1d	±7d	±7d
Baseline condition	X					
Physical examination	X	X	(X) ⁵	(X) ⁵	(X) ⁵	(X) ⁵
Vital signs	X	X	(X) ⁵	(X) ⁵	(X) ⁵	(X) ⁵
Pregnancy test ⁴	X					
Infection testing ⁶	X					
Safety laboratory tests (Local lab) ⁷	X		(X) ⁵	(X) ⁵	(X) ⁵	(X) ⁵
Nucleic acid testing	X					
COVID-19 symptoms		(X)	(X)	(X)	(X)	(X)
Review of in-/exclusion criteria	X	X				
IRT transaction	X	X	X			
Dispense/administration study drug		X	X			
Adverse events	X	X	X	X	X	X
Concomitant therapy	X	X	X	X	X	X
[REDACTED]						
Study Completion						X

Abbreviations: EoS: end of study; IRT: Interactive Response Technology; V: Visit.

- 1: Visit 1 and Visit 2 can be on the same day. If V1 and V2 is performed on the same day, the procedures do not need to be repeated.
- 2: V3 is an additional visit. There's a possibility that patient will receive [REDACTED] of spesolimab at V3 [REDACTED] if his flare symptoms persist after the [REDACTED] dose. If in that case, the visit schedule will be changed to approximately at [REDACTED] after initial dose of spesolimab.
- 3: Should a patient prematurely discontinue from the treatment; every effort should be made to keep the patient in the trial and complete all of the remaining study visits. If a patient is not willing to follow the whole visit schedule, the EOS Visit (Visit 6) should be conducted at [REDACTED] weeks after the last spesolimab administration at a minimum. If patients refuse to return to the study site, early EoS visit should be completed at the timing of prematurely discontinuation and then at least safety information should be collected by phone at [REDACTED] weeks after the last spesolimab administration.
- 4: Only applicable for women of childbearing potential.
- 5: Physical examination, vital signs and safety laboratory test shown with parentheses "(X)" are optional and will be performed according to standard clinical practice and when deemed appropriate by the investigator.

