6.3 SUBJECT SETS ANALYSED

The following analysis set will be defined for this trial:

- **Enrolled Set (ES):**
This patient set includes all patients who signed informed consent. It will be used for analyses of patient disposition.
- **Treated Set (TS):**
This patient set includes all patients who received at least one dose of study drug. It will be used for all other analyses.

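### The Day 8 local tolerability percentage names no denominator, so the SAP default divides by all treated patients, including any who had no second administration

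*SAP*

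**What the plan says.** The table is specified in SAP 7.8.5: "Local Tolerability will be summarized at Day 1 and Day 8, with the frequency and percentage of patients/flare treatment periods", for any reaction, by symptom and severity. The section does not say who is in the denominator at either day, and the slash leaves the unit of analysis open.

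Two general statements in SAP 7 bear on it. For categorical tabulations the percentage base is "unless otherwise specified, all patients in the respective patient set whether they have non-missing values or not". For safety data the analysis is per patient, "whose denominator will be the number of patients or time at risk per patient for all applicable periods". SAP 7 adds that a category for missing values is displayed when there are any.

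The patient set follows from SAP 6.3, on the Treated Set: "This patient set includes all patients who received at least one dose of study drug. It will be used for all other analyses". Disposition, which uses the Enrolled Set, is the exception.

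Protocol 3.1 makes the second administration conditional: "If deemed necessary by the treating physician (i.e. if the flare symptoms persist". The flow-chart footnote treats the visit in the same way: "V3 is an additional visit. There's a possibility that patient will receive". The days of administration are redacted in Protocol 3.1 and SAP 6.1. Day 8 itself is legible only in SAP 7.8.5 and in the account of the earlier randomised trial in Protocol 1.2.3.

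**The concern.** A local reaction to a second administration can occur only in someone who received one. If the percentage is taken over everyone with at least one dose, patients treated only once enlarge the denominator and can add nothing to the numerator. The result is the share of all treated patients who were re-dosed and also reacted. A reader will take it for the reaction rate after a second administration.

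Collecting further safety and tolerability data is the program's stated secondary aim (Protocol 2.1.1), and this is the only output visible in the SAP that carries tolerability in its name. The Day 1 and Day 8 percentages will be reported together, and readers will compare them whether or not the plan intends it. On the default rule they share a base that is right for Day 1 and too large for Day 8.

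**Working it through.** **Which denominator applies**

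1. SAP 7.8.5 specifies no denominator, so the default in SAP 7 is not displaced.
2. The default counts all patients in the set, including those without a value.
3. The set is the Treated Set, which requires one dose and not two (SAP 6.3).
4. The second administration is optional (Protocol 3.1 and 6.1.2).

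Together these divide Day 8 reactors by all treated patients. The default is worded for patients. For a percentage of flare treatment periods no default is written, and the parallel reading is all periods.

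**Formula**

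Let N be the number treated, m the number given a second administration, r the number of these who react, and s = m/N.

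- Printed percentage under the default: r/N
- Rate among those re-dosed: r/m
- Ratio of the second to the first: (r/m)/(r/N) = N/m = 1/s

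The plan states no Day 8 rate, no expected s and no sample size (Protocol 3.2.1 sets no recruitment goal). There is no figure of its own to reproduce.

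**An assumed value for s**

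The only related figure in the documents concerns the earlier randomised trial (Protocol 1.2.3): "At day 8, 12 patients randomized to spesolimab received an open-label (second) dose of 900 mg spesolimab". The arm size is not printed but follows from the printed percentages. 19 patients = 54.3%, 15 = 42.9%, 16 = 45.7%, 23 = 65.7%, 13 = 37.1%, 18 = 51.4% and 21 = 60.0% each fit only N = 35. For placebo, 1 = 5.6% and 2 = 11.1% fit only N = 18, and 35 + 18 = 53, the stated total.

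- s = 12/35 = 34.3%
- Factor = 35/12 = 2.92
- Exact (Clopper-Pearson) 95% CI for s: 19.1% to 52.2%
- Factor over that interval: 1/0.522 = 1.9 to 1/0.191 = 5.2

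**Other assumed values**

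| s | factor 1/s |
|---|---|
| 20% | 5.0 |
| 34.3% | 2.9 |
| 50% | 2.0 |
| 70% | 1.4 |
| 100% | 1.0 |

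**Illustration with assumed counts**

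With 35 treated, 12 re-dosed and 3 reactors at Day 8, the default gives 3/35 = 8.6%. Among those re-dosed it is 3/12 = 25.0%. If the other 35 − 12 = 23 patients were shown as missing, the printed figure would still be 8.6%, because the base remains 35.

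**The case against.** Several points on the other side carry weight.

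**Missing values.** A reader might infer that patients without a second administration are counted as free of reaction. The SAP does not say so. They could appear in a row for missing values, which would let an attentive reader rebuild the denominator. That stands, but it leaves the printed percentage unchanged, and the SAP does not say whether a patient who was not due a dose is missing or not applicable. The exposure tables would not fill the gap. SAP 7.7 summarises number of doses per patient over all flares combined, so with re-entry allowed it does not show who had a second dose within a flare.

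**The safety-specific rule.** The wording about applicable periods in SAP 7 might be read as a narrower denominator. It concerns patients or their time at risk over treatment periods and does not limit the base to those dosed on a given day. At best the text is open to two readings, which also calls for a stated denominator.

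**What Day 8 means.** Because the days are redacted, Day 8 as the day of the second administration is an inference. If Day 8 also records late or persisting reactions to the first dose, an all-treated base is partly right. The SAP would then need to say so, because one table would mix two groups at risk.

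**Direction.** A reader might infer that a true rise in reactions would be printed as a fall. That depends on the rates. With an assumed 10% at Day 1 and 20% among those re-dosed, s = 12/35 would print 20% × 12/35 = 6.9% at Day 8, and reversal needs s below 50%. With s = 12/35, a true rise of more than 2.9-fold would still appear as a rise. No Day 1 versus Day 8 comparison is planned, and patients with persisting flares are a selected group, so the comparison would be confounded even on the right base.

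**Collection of the data.** A reader might also infer from Protocol 5.2 that local tolerability is not assessed at all. That cannot be settled, because a row of the flow chart is redacted. It forms no part of this point.

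**Conclusion.** The point holds as a minor one. Under the SAP's own default, the Day 8 percentage is taken over all treated patients and understates the reaction rate among those given a second administration by 1/s whenever s is below 100%. This rests on two assumptions: that Day 8 is the day of the optional second administration, and that nothing in internal standards replaces the written default.

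The size is not known for this program. A threefold dilution is tempting to quote, but it borrows 12 of 35 from a different trial. The interval of 1.9 to 5.2 reflects sampling error in that trial only, and not whether its re-dosing share carries over to expanded access.

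The consequence is confined to one descriptive table. Local tolerability is neither a primary nor a secondary endpoint, no hypothesis is tested, and the count of reactors is printed beside the percentage.

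**What to change.** Add one sentence to SAP 7.8.5: at each day, the denominator is the patients given spesolimab on that day who had local tolerability assessed, and that N is shown in the table. Choose one unit, patients or flare treatment periods, or show both in separate columns, each with its own N. If Day 8 is also meant to capture reactions to the first dose, report those separately.

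The cost is small. It needs one sentence and a change to one table, and no new data where the assessment is already made. The Day 8 figure will rest on a smaller N, be less precise and look less favourable.
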